### 11.3. Planned Interim Analyses

Immunogenicity and safety results will be provided for the purpose of planning subsequent trials as described in Sections 11.3.1 and 11.3.2. Interim analyses would only be used to terminate this trial in the event that unanticipated safety events deemed to be of sufficient concern require such action by the sponsor. These assessments will not be made on the basis of testing a formal statistical hypothesis; therefore, p-value adjustment will not be made to any analyses. An SMC will be convened by DMID to review study progress and participant, clinical, safety, and reactogenicity data.

#### 11.3.1 Interim Safety Review

Reports for interim safety review may include enrollment, and demographic information, dosing, solicited and unsolicited AE/SAE data, and clinical laboratory results. Additional data may be requested by the SMC, and interim statistical reports may be generated as deemed necessary and appropriate by DMID. The SMC may receive data in aggregate and presented by treatment arm. The SMC may also be provided with expected and observed rates of the expected AEs, and may request the treatment assignment be unblinded for an individual subject if required for safety

assessment. The SMC will meet and review this data at scheduled time points or ad hoc as needed during the study as defined in the SMC charter. As an outcome of each review/meeting, the SMC will make a recommendation as to the advisability of proceeding with study vaccinations (as applicable), and to continue, modify, or terminate this trial.

Additional safety data may be requested by the vaccine partner during study follow-up for the purpose of planning future trials. Interim statistical reports may be generated as deemed necessary and appropriate by DMID. Reports may include data summarized by unblinded treatment arm; if so, the presentation will be in a format that prevents inadvertent unblinding of any individual subject. Such reports will be made available to the sponsor and vaccine partner for planning subsequent trials. These analyses will not be used to make any decisions concerning the conduct of this trial. No hypothesis testing will be included in any interim report. Additionally, the study will be monitored to determine if any of the halting rules described in [Section 9.5](#) are met.

#### **11.3.2. Interim Immunogenicity Review**

An interim report of blinded MN results will be provided after the 19 subjects enrolled in 2018 have completed the Day 113 visit. This streamlined report will be made available to the sponsor and vaccine partner for planning subsequent trials. These results will not be used to make any decisions concerning the conduct of this trial. No hypothesis testing will be included in any interim analysis.

#### **11.4. Final Analysis Plan**

Once the last subject completes the last immunogenicity outcome visit (approximately 21 days after the second study vaccination), all serum samples will be sent for secondary immunogenicity assays (HAI, MN, and sIgA). After such data are reported in the database, and the data are considered clean and complete, a “topline” subset of the immunogenicity tables planned for the CSR will be provided to DMID on an expedited timeline.

Once the last subject completes the last clinical visit (approximately 275 days after the second study vaccination), the clinical database will be cleaned, monitored and locked. Unblinded analyses of safety, reactogenicity, and immunogenicity will be performed by the SDCC after the primary clinical database is locked and all immunogenicity data are received.

Analysis of exploratory immunogenicity endpoints may be performed and released as the data are available from the research laboratory. Any such analyses would be considered the final analysis for the endpoint and included in the CSR. Additional exploratory immunogenicity

endpoint data not available at the time of CSR preparation may be included in an addendum to the CSR. A formal statistical analysis plan will be developed and finalized prior to clinical and laboratory database freeze for the interim analysis, which will define the analyses to be included in the interim analysis and the final CSR.

#### **11.4.1. Analysis Populations**

The Safety Analysis population includes all subjects who received at least one dose of study vaccine.

The modified intent-to-treat (mITT) population includes all subjects who received at least one dose of study vaccine and contributed both pre- and at least one post-study vaccination venous blood samples for immunogenicity testing (HAI antibody assays) for which valid results were reported. For analyses using the mITT population, subjects will be grouped based on randomized treatment arm.

The per protocol (PP) population includes all subjects in the mITT subset with the following exclusions:

- Data from all available visits for subjects found to be ineligible at baseline.
- Data from all visits subsequent to major protocol deviations, such as:
  - Second study vaccination not received,
  - Second study vaccination received out of window,
  - Receipt of non-study licensed live or inactivated vaccine within 30 days prior to the first study vaccination,
  - Receipt of influenza vaccine (live or inactivated) within 6 months prior to the first study vaccination.
- Receipt of immunosuppressive therapy (e.g., corticosteroids)
  - Receipt of aspirin or salicylate-containing products
  - Receipt of antiviral therapy
- Data from any visit that occurs substantially out of window, such that in the opinion of the study investigator could affect the scientific goals of this protocol.

For analyses using the PP population, subjects will be grouped based on study vaccinations received.

#### **11.4.2. Primary Safety Data**

Summaries and analysis of safety data will be presented for the Safety Analysis Population.

Solicited AEs will be summarized by severity for each day after the first study vaccination (Days 1-8 post vaccination) and as the maximum severity over all 8 days. Additionally, solicited AEs will be analyzed by taking the most severe response over the follow-up period, dichotomizing into a binary variable (none versus mild, moderate, or severe) and using standard techniques, such as exact confidence intervals, to summarize the number and percentage of subjects reporting each symptom, any upper respiratory symptom and any systemic symptom by treatment arm.

Unsolicited AEs will be coded by Medical Dictionary for Regulatory Activities (MedDRA®) for preferred term and system organ class (SOC). The number of SAEs, AESIs, and NOCMCs is expected to be small in this trial and will be reported by detailed listing showing the event description, MedDRA preferred term and SOC, relevant dates (study vaccinations and AEs), severity, relatedness, and outcome for each event. If more than 5% of subjects report SAEs, and AESIs, and NOCMCs then the number and percentage of subjects reporting each type of event will be reported by treatment arm and compared using Fisher's Exact test. Unsolicited AEs will be summarized as number and percentage of subjects reporting at least one event in each MedDRA preferred term and SOC, cross tabulated by severity and relationship to study product. Additionally, the proportion of subjects and exact 95% confidence intervals of AEs in aggregate and by MedDRA categories will be computed.

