## 5.2. Subject Exclusion Criteria

Subjects eligible to participate in this study must not meet any of the following exclusion criteria:

1. Have an acute illness, as determined by the site PI or appropriate sub-investigator, within 72 hours prior to each study vaccination.

*An acute illness which is nearly resolved with only minor residual symptoms remaining is allowable if, in the opinion of the site PI or appropriate sub-investigator, the residual symptoms will not interfere with the ability to assess safety parameters as required by the protocol.*

2. Have any medical disease or condition that, in the opinion of the site PI or appropriate sub-investigator, is a contraindication to study participation.

*Including acute or chronic medical disease or condition, defined as persisting for at least 90 days, that would place the subject at an unacceptable risk of injury, render the subject unable to meet the requirements of the protocol, or may interfere with the evaluation of responses or the subject's successful completion of this study.*

3. Have immunosuppression as a result of an underlying illness or treatment, or use of anticancer chemotherapy or radiation therapy (cytotoxic) within 3 years prior to study vaccination.
4. Have known active neoplastic disease or a history of any hematologic malignancy. Non-melanoma skin cancers that are not active are permitted.
5. Have known HIV, hepatitis B, or hepatitis C infection.
6. Have a history of severe reactions following previous immunization with licensed or unlicensed influenza vaccines.
7. History of anatomic disorder of the nares or nasopharynx (Deviated septum is allowed).
8. History of chronic sinus infections.
9. Have a history of Guillain-Barré Syndrome.
10. Have a history of alcohol or drug abuse prior to study vaccination.
11. Have any diagnosis, current or past, of schizophrenia, bipolar disease, or other psychiatric diagnosis that may interfere with subject compliance or safety evaluations.
12. Have been hospitalized for psychiatric illness, history of suicide attempt, or confinement for danger to self or others prior to study vaccination.
13. Have taken oral and/or nasal corticosteroids of any dose within 30 days prior to each study vaccination or plan to take in the 30 days following the first study vaccination.

- 
14. Have taken high-dose inhaled corticosteroids within 30 days (prior to study vaccination).  

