- Approximately 16 mL of PBMCs will be collected for IFN- $\gamma$  ELISPOT and CFSE dilution/ICS assays.
- A urine pregnancy test will be performed on all female adolescent subjects of childbearing potential and must be negative to ensure eligibility.
- Subjects will be enrolled in AdvantageEDCSM and assigned randomly to a treatment arm prior to the first study vaccination.
- Pre-administration reactogenicity assessments will be performed prior to the first study vaccination to establish baseline. Subjects will then receive a single dose of study product or placebo intranasally. Subjects will be observed in the clinic for at least 30 minutes after the first study vaccination. Post-administration reactogenicity assessments will be completed, and any AE/SAEs will be recorded on the appropriate data collection form prior to discharge from the clinic.
- Parent(s)/legal guardian(s) will be provided with a memory aid and other study-related materials to record daily oral temperature, solicited systemic reactions, any unsolicited AEs, and concomitant medications. Parent(s)/legal guardian(s) will be encouraged to take child's oral temperature around the same time each day. Subjects must not eat or drink anything hot or cold, or smoke within 10 minutes prior to taking oral temperature. Parent(s)/legal guardian(s) will be instructed on how to use their memory aid and how to measure and record AEs prior to discharge from the clinic. Parent(s)/legal guardian(s) will be instructed to notify the study center if they develop any severe reactions after the first study vaccination. If the site principal investigator or appropriate sub-investigator deems the reaction severe enough, further instructions will be given to the parent(s)/legal/guardian(s) on the proper course of action, including a return to the clinic for immediate evaluation if appropriate.

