### 9.2 Methods and Timing for Assessing, Recording, and Analyzing Safety Parameters

#### 9.2.1 Adverse Events

**Adverse Event (AE):** ICH E6 defines an AE as any untoward medical occurrence in a patient or clinical investigation subject administered a pharmaceutical product regardless of its causal relationship to the study treatment. An AE can therefore be any unfavorable and unintended sign (including an abnormal laboratory finding), symptom, or disease temporally associated with the

use of a medicinal (investigational) product. The occurrence of an AE may come to the attention of study personnel during study visits and interviews of a study recipient presenting for medical care, or upon review by a study monitor.

AEs, including solicited local (respiratory) and systemic (subjective and quantitative) reactions, not meeting the protocol-defined criteria for SAEs will be captured on the appropriate data collection form and eCRF. Information to be collected for unsolicited non-serious AEs includes event description, date of onset, licensed study physician's assessment of severity and relationship to study product and alternate etiology (if not related to study product) (assessed only by those with the training and authority to make a diagnosis and listed on the Form FDA 1572 as the site principal investigator or sub-investigator), date of resolution of the event, seriousness, and outcome. AEs occurring during the trial collection and reporting period will be documented appropriately regardless of relationship. AEs will be followed through resolution.

Any medical condition that is present at the time that the subject is screened will be considered as baseline and not reported as an AE. However, if the severity of any pre-existing medical condition increases, it will be recorded as an AE.

AEs must be graded for severity and assessed for relationship to study product (see definitions below). AEs characterized as intermittent require documentation of onset and duration of each episode. The start and stop date of each reported AE will be recorded on the appropriate data collection form and eCRF.

FDA defines an AE as any untoward medical occurrence associated with the use of a drug in humans, whether or not considered drug related.

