#### **Local (Upper Respiratory) Reactogenicity Grading**

Local (Nasal) Reaction	Mild (Grade 1)	Moderate (Grade 2)	Severe (Grade 3)
Runny Nose	Noticeable but does not interfere with daily activity	Moderate discomfort/interferes with daily activity	Significant discomfort/prevents daily activity or seeks medical encounter

Local (Nasal) Reaction	Mild (Grade 1)	Moderate (Grade 2)	Severe (Grade 3)
Stuffy Nose/Congestion	Noticeable but does not interfere with daily activity	Moderate discomfort/interferes with breathing from nose	not being able to breath from nose, or prevents daily activity or seeks medical encounter
Sneezing	Noticeable but does not interfere with daily activity	Moderate discomfort. Interferes with daily activity	Significant discomfort/prevents daily activity
Nasal Pain/Irritation	Noticeable but does not interfere with daily activity	Moderate discomfort/interferes with daily activity	Significant discomfort/prevents daily activity or seeks medical encounter
Nasal Bleeding/Epistaxis	Total duration of all episodes in a 24 hour period <30 minutes	Total duration of all episodes in a 24 hour period $\geq$ 30 minutes	Any bleeding that required visit for medical encounter
Sinus Pressure/Pain	Noticeable but does not interfere with daily activity	Moderate discomfort. Interferes with daily activity	Significant discomfort/prevents daily activity
Sore Throat/Sore/Scratchy/ Itchy or Painful Throat	Noticeable but does not interfere with eating and/or drinking	Moderate discomfort. Interferes with eating and/or drinking	Significant discomfort/prevents eating and/or drinking or seeks medical encounter
Cough	Noticeable but does not interfere with daily activity or sleeping	Moderate discomfort/interferes with daily activity or sleeping	Significant discomfort/prevents daily activity or seeks medical encounter
Trouble breathing/Shortness of Breath	Noticeable but does not interfere with daily activity or not	Moderate discomfort/interferes with daily activity or	Significant discomfort/prevents daily activity or seeks

Local (Nasal) Reaction	Mild (Grade 1)	Moderate (Grade 2)	Severe (Grade 3)

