9.3.1. Solicited Events and Symptoms

Systemic and upper respiratory (local) solicited adverse events were collected pre-vaccination, and systemic and local solicited adverse events were collected 30 minutes post-vaccination and then daily for 7 days after first vaccination and graded on a scale of 0 (absent), 1 (mild), 2 (moderate) and 3 (severe). Systemic events include: fever, feverishness (chills/shivering/sweating), fatigue (tiredness), malaise (general unwell feeling), myalgia (body aches/muscular pain), arthralgia (joint pain), headache, flushing, decreased activity, decreased appetite, abdominal pain, nausea, vomiting, diarrhea, eye pruritus, eye redness (conjunctivitis), and allergy. Local events include: runny nose, stuffy nose/congestion, sneezing, nasal pain/irritation, nasal bleeding/epistaxis, sinus pressure/pain, sore throat/sore/scratchy/itchy or painful throat, cough, trouble breathing/shortness of breath. Wheezing experienced on or before Day 8 is considered a solicited event. The grading scales for solicited systemic and local (upper respiratory) adverse events are provided in [Table 7](#) and [Table 6](#), respectively. Grading for wheezing events is provided in [Table 9](#).

The proportion of subjects reporting at least one solicited adverse event will be summarized for each solicited adverse event, any systemic symptom, any local symptom, and any symptoms. The 95% CI calculated using Blaker methodology from a binomial distribution (SAS Proc Freq with a binomial option) will be presented ([Table 40](#)).

For each systemic and local event, any systemic event, any local event, and any solicited event, the maximum severity over 7 days after first vaccination will be summarized for the Safety population. The number and percentage of subjects reporting each event will be summarized by the maximum severity and study group. For each event the denominator is the number of subjects with non-missing data for the specific event ([Table 42](#)).

The number of subjects reporting a solicited adverse event will be summarized for each day post vaccination in a summary table ([Table 43](#) and [Table 44](#)) and graphically in a bar chart ([Figure 50](#) and [Figure 51](#)). The difference proportion of subjects experiencing any individual symptom, any local or systemic symptom, and any symptom overall will be presented in [Table 41](#).

Solicited adverse events by subject will be presented in [Listing 11](#) and [Listing 12](#).

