	Moderate	x	xx	xx,xx	x	xx	xx,xx
	Severe	x	xx	xx,xx	x	xx	xx,xx

Note: N = Number of subjects in the Safety Population. Severity is the maximum severity reported over all solicited symptoms post dosing for each subject.

Table 43: Number and Percentage of Subjects Experiencing Solicited Events by Symptom, Severity and Day Post First Vaccination – M2SR Recipients, Safety Population

Symptom	Severity	Pre-Dose		Post-Dose		Day 1		Day 2		Day 3		Day 4		Day 5		Day 6		Day 7		Day 8+	
		n	%	n	%	n	%	n	%	n	%	n	%	n	%	n	%	n	%	n	%
Any Symptom	None	x	xx	x	xx	x	xx	x	xx	x	xx	x	xx	x	xx	x	xx	x	xx	x	xx
	Mild	x	xx	x	xx	x	xx	x	xx	x	xx	x	xx	x	xx	x	xx	x	xx	x	xx
	Moderate	x	xx	x	xx	x	xx	x	xx	x	xx	x	xx	x	xx	x	xx	x	xx	x	xx
	Severe	x	xx	x	xx	x	xx	x	xx	x	xx	x	xx	x	xx	x	xx	x	xx	x	xx
	Not Reported	x	xx	x	xx	x	xx	x	xx	x	xx	x	xx	x	xx	x	xx	x	xx	x	xx
Systemic Symptoms																					
Any Systemic Symptom	None	x	xx	x	xx	x	xx	x	xx	x	xx	x	xx	x	xx	x	xx	x	xx	x	xx
	Mild	x	xx	x	xx	x	xx	x	xx	x	xx	x	xx	x	xx	x	xx	x	xx	x	xx
	Moderate	x	xx	x	xx	x	xx	x	xx	x	xx	x	xx	x	xx	x	xx	x	xx	x	xx
	Severe	x	xx	x	xx	x	xx	x	xx	x	xx	x	xx	x	xx	x	xx	x	xx	x	xx
	Not Reported	x	xx	x	xx	x	xx	x	xx	x	xx	x	xx	x	xx	x	xx	x	xx	x	xx
Feverishness (Chills/Shivering/Sweating)	None	x	xx	x	xx	x	xx	x	xx	x	xx	x	xx	x	xx	x	xx	x	xx	x	xx
	Mild	x	xx	x	xx	x	xx	x	xx	x	xx	x	xx	x	xx	x	xx	x	xx	x	xx
	Moderate	x	xx	x	xx	x	xx	x	xx	x	xx	x	xx	x	xx	x	xx	x	xx	x	xx
	Severe	x	xx	x	xx	x	xx	x	xx	x	xx	x	xx	x	xx	x	xx	x	xx	x	xx
	Not Reported	x	xx	x	xx	x	xx	x	xx	x	xx	x	xx	x	xx	x	xx	x	xx	x	xx
Fatigue (Tiredness)	None	x	xx	x	xx	x	xx	x	xx	x	xx	x	xx	x	xx	x	xx	x	xx	x	xx
	Mild	x	xx	x	xx	x	xx	x	xx	x	xx	x	xx	x	xx	x	xx	x	xx	x	xx
	Moderate	x	xx	x	xx	x	xx	x	xx	x	xx	x	xx	x	xx	x	xx	x	xx	x	xx

Table 43: Number and Percentage of Subjects Experiencing Solicited Events by Symptom, Severity and Day Post First Vaccination – M2SR Recipients, Safety Population (Continued)

Symptom	Severity	Pre-Dose		Post-Dose		Day 1		Day 2		Day 3		Day 4		Day 5		Day 6		Day 7		Day 8+	
		n	%	n	%	n	%	n	%	n	%	n	%	n	%	n	%	n	%	n	%
	Severe	x	xx	x	xx	x	xx	x	xx	x	xx	x	xx	x	xx	x	xx	x	xx	x	xx
	Not Reported	x	xx	x	xx	x	xx	x	xx	x	xx	x	xx	x	xx	x	xx	x	xx	x	xx
Malaise (General Unwell Feeling)	None	x	xx	x	xx	x	xx	x	xx	x	xx	x	xx	x	xx	x	xx	x	xx	x	xx
	Mild	x	xx	x	xx	x	xx	x	xx	x	xx	x	xx	x	xx	x	xx	x	xx	x	xx
	Moderate	x	xx	x	xx	x	xx	x	xx	x	xx	x	xx	x	xx	x	xx	x	xx	x	xx
	Severe	x	xx	x	xx	x	xx	x	xx	x	xx	x	xx	x	xx	x	xx	x	xx	x	xx
	Not Reported	x	xx	x	xx	x	xx	x	xx	x	xx	x	xx	x	xx	x	xx	x	xx	x	xx

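### Solicited-event rates count any post-dose grade of 1 or more without using the pre-dose grade, so unchanged pre-dose symptoms score as events

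*Protocol*

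**What the plan says.** **The counting rule.** Protocol 11.4.2 takes the most severe response over follow-up, "dichotomizing into a binary variable (none versus mild, moderate, or severe". SAP 9.3.1 has: "The proportion of subjects reporting at least one solicited adverse event will be summarized for each solicited adverse event". The note to SAP Table 42 reads: "Severity is the maximum severity reported over all solicited symptoms post dosing for each subject". None of these has a condition on new onset or worsening. The threshold is low. For runny nose, sneezing and several other local symptoms, Grade 1 begins at "Noticeable but does not interfere with daily activity" (Protocol 9.2.2).

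**The baseline.** Protocol 7.3.1 states: "Pre-administration reactogenicity assessments will be performed prior to the first study vaccination to establish baseline". SAP 9.3.1 confirms that systemic and local symptoms are collected before vaccination. The pre-dose grades appear in the Pre-Dose column of Tables 43 and 44 and, child by child, in Listings 11 and 12.

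**Who may be dosed.** Footnote 4 in Protocol 5.2 says "An acute illness which is nearly resolved with only minor residual symptoms remaining is allowable", provided that in the investigator's opinion "the residual symptoms will not interfere with the ability to assess safety parameters as required by the protocol". Exclusion 25 bars signs or symptoms that could confound the reactogenicity assessment, and its footnote defers vaccination until they resolve.

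**Other adverse events.** Protocol 9.2.1 treats a medical condition present at screening as baseline and adds: "However, if the severity of any pre-existing medical condition increases, it will be recorded as an AE".

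**The concern.** The trial records the reading that would separate a new reaction from a symptom the child already had, and then leaves it out of every rate. A child with Grade 1 congestion before dosing and the same Grade 1 congestion afterwards counts as having a local solicited event in Tables 40 to 42.

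Nothing later in the plan takes that child out. Tables 43 and 44 give pre-dose grades as counts by arm and do not link them to the same child's later grades. Listings 11 and 12 make the link visible but produce no rate. Listing 11 records alternate etiology for Grade 3 events only, and Listing 12, for local symptoms, has no such column.

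Two quantities are at stake: each arm's rate, which is pushed upward, and the Table 41 difference between arms, which is pulled toward zero when a true difference exists.

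**Working it through.** **The plan's own figures.** The documents give no figure for carry-over of pre-dose symptoms. Their only safety calculation is Table 3, the chance of at least one event, 1 − (1 − p)^n. For n = 25 and n = 50 it gives 92.8% and 99.5% at p = 10%, 22.2% and 39.5% at 1%, 2.5% and 4.9% at 0.1%, and 0.25% and 0.50% at 0.01%. These agree with the printed table, which is not in dispute.

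**Model.** Let t be the rate of new or worsened symptoms in an arm. Let c be the fraction of children with a pre-dose symptom that persists unchanged after dosing. Take c as independent of t and, by randomization, equal in expectation in both arms.

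- Observed rate under the plan's rule: t + (1 − t)c
- Observed difference: (t_M2SR − t_placebo)(1 − c)
- Net extra children counted per arm: 25(1 − t)c

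**Inputs.** The 25 per arm is from Protocol Table 1. The rest are assumptions: pre-dose prevalence of any local symptom of 5% to 20%, persistence after dosing of 70% to 90%, and illustrative rates of 30% (placebo) and 50% (M2SR). Then c runs from 0.05 × 0.7 = 3.5% to 0.20 × 0.9 = 18%.

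| | c = 3.5% | c = 18% |
|---|---|---|
| Placebo, true 30% | 0.30 + 0.70 × 0.035 = 32.45% | 0.30 + 0.70 × 0.18 = 42.6% |
| M2SR, true 50% | 0.50 + 0.50 × 0.035 = 51.75% | 0.50 + 0.50 × 0.18 = 59.0% |
| Difference, true 20 points | 20 × 0.965 = 19.3 | 20 × 0.82 = 16.4 |
| Net extra placebo children of 25 | 25 × 0.70 × 0.035 = 0.6 | 25 × 0.70 × 0.18 = 3.2 |

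**A second set of assumptions.** With t = 20% in both arms and c = 4%, 8%, 12% and 20%, each arm's observed rate is 23.2%, 26.4%, 29.6% and 36.0%, which is 0.8, 1.6, 2.4 and 4.0 extra children per arm. The difference stays at zero throughout. With 40% against 20%, the true 20 points is observed as 19.2, 18.4, 17.6 and 16.0.

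**Persistence.** SAP 9.3.1 has symptoms graded 30 minutes after dosing and then daily. A symptom present just before dosing will often still be there at the first post-dose reading, so high persistence is plausible, but the documents do not state it.

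**Fever is not affected.** Entry requires an oral temperature below 100.0°F, and Grade 1 fever starts at 100.4°F.

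**The case against.** The strongest objection is that the example child should rarely be dosed. Footnote 4 is conditional, and exclusion 25 with its deferral footnote is aimed at exactly the symptoms that would cloud a reactogenicity reading. This stands as a limit on frequency and makes the top of the assumed range for c less likely. It does not remove the problem: both rules depend on judgement, and under the present count any residual solicited symptom that persists scores automatically.

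Second, counting every post-dose symptom against a blinded placebo arm is a defensible conservative choice in a pediatric Phase I study. A strict rule of grade above baseline can miss a real reaction at the same grade, or a symptom that resolved and came back. This also stands, and it is why the any-grade count should not be replaced.

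Third, the dilution is small beside sampling error. At 50% against 30% with 25 per arm, the 95% half-width is 1.96 × √(0.25/25 + 0.21/25) = 26.6 points. That is correct for the difference. It does not excuse the upward bias in the single-arm rates, which Table 40 reports.

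Some stronger readings are tempting but not supported:

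- That M2SR is made to look more reactogenic than placebo. Randomization gives zero bias in the difference under no effect and dilution otherwise. A chance imbalance of one child moves an arm by up to 1/25 = 4 points, and the Table 41 interval reflects such chance variation.
- That the SAP expects pre-dose symptoms because the Pre-Dose column has Mild, Moderate and Severe rows. The shell repeats the same rows under every time point.
- That the count contradicts Protocol 9.2.1. That rule concerns conditions present at screening, which may be up to 28 days before dosing, so it does not settle symptoms that arise in between.
- That enrollment fell in a season of common respiratory symptoms. The documents do not establish this. SAP 4.1 and 12 describe a pause in November 2018 and a restart in 2019, timed so that QIV is given before the influenza season.

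**Conclusion.** The point holds as a gap in the derivation. Pre-dose grades are collected and displayed, but no solicited-event rate uses them, so an unchanged pre-dose symptom counts as an event. The consequence is an upward bias in each arm's rate and dilution of a true M2SR–placebo difference by the factor 1 − c, with no arm difference created in expectation.

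The size rests wholly on c, which the documents do not give, and on carry-over being independent of new reactions. Over the assumed 3.5% to 18%, a 30% rate reads as about 32% to 43% and a 20-point difference as 19.3 to 16.4 points. If footnote 4 and exclusion 25 are applied strictly, c could fall below this range. This is a worthwhile improvement to the reporting of a primary endpoint, not a flaw that invalidates the comparison.

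**What to change.** Leave eligibility and the any-grade post-dose count as they are. Then:

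1. Add to Tables 40 and 42 a new-or-worsened count: a child counts for a symptom when the highest post-dose grade through Day 8 exceeds that child's own pre-dose grade for the same symptom. Build the any-local, any-systemic and any-symptom rows from these symptom-level flags.
2. Add the corresponding difference and 95% CI to Table 41.
3. State in SAP 9.3.1 how each count is interpreted: the any-grade count as all symptoms observed after dosing, the new-or-worsened count as the estimate with pre-existing symptoms removed.

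The cost is a few lines of SAP text and one derived flag from data already collected. The drawbacks are two versions of each rate in the CSR, and a new-or-worsened count that can miss same-grade reactions and recurrences. Keeping the any-grade count beside it covers the second drawback.
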